### **3.2.5 VNS Use**

Patients will be considered to have VNS use if the answer to the CRF question "Has a VNS magnet been used?" is equal to "Yes".

### **3.3 Definition of Baseline values**

In this NIS, Baseline is defined as the data collected at Visit 1. For prior and concomitant medications and for AED drug load, Baseline is defined as first BRV administration. For seizure frequency variables, Baseline is defined in [Section 8.2.2.1](#).

### **3.4 Protocol deviations**

Important protocol deviations are deviations from the protocol which potentially could have a meaningful impact on study conduct or on the primary effectiveness or key safety/tolerability for an individual patient. The criteria for identifying important protocol deviations will be defined within the appropriate protocol-specific documents. Important protocol deviations will be reviewed as part of the ongoing data cleaning process and data evaluation. In addition, prior to database lock, all important protocol deviations will be reviewed during the data evaluation meeting (DEM), in order to confirm exclusion from the study analysis sets defined in [Section 3.5](#).

### **3.5 Analysis sets**

The All Subjects Documented set is defined as all patients included in the study with valid data consent and for whom at least Visit 1 (Baseline) is documented. The All Subjects Documented set will be used for patient disposition and patient data listings only.

The Safety Set (SS) is defined as all patients included in the All Subjects Documented set for whom it cannot be excluded that they received treatment with BRV at least once in the study. Evidence of BRV dosing will be determined based on patients meeting 1 or more of the following criteria:

- At least 1 entry with a total daily dose >0 recorded in the BRV Medication (NIS) CRF page
- A present date of first BRV administration during observational study, recorded in the First Administration of BRV CRF page
- A present date of last BRV administration while in the study, recorded in the Study Termination (Dropout) or Study Termination (Completed Subject) CRF pages

The SS will be used for the summary of the safety data, Baseline characteristics of the patients, and important protocol deviations.

The Full Analysis Set (FAS) is defined as all patients in the SS who did not receive BRV before entering this NIS. Any patients with a documented protocol violation of Selection Criterion #1 will be considered to have been treated with BRV prior to inclusion in this NIS and will be excluded from the FAS. The FAS will be used for the analysis of BRV retention (ie, the primary variable), the secondary variables, and other variables.

The modified FAS is defined as all patients in the FAS who are treated according to the approved SmPC during their Observation Period, representing the on-label use of BRV. Compliance with the approved SmPC is defined as follows:

- Patient has POS with or without secondary generalization at Baseline (ie, patient does not have a protocol violation of Selection Criterion #5)
- All documented BRV doses were less than or equal to the maximum approved dose of 200mg/day
- BRV doses were greater than or equal to the minimum approved dose of 50mg/day (with the exception of down-titrating). Per the SmPC, a down-titration of BRV is allowed to 20mg/day, hence any patients receiving BRV doses lower than 50mg/day from day 2 onwards will be reviewed during the DEM to determine whether they are taking BRV per SmPC.
- BRV doses were administered in 2 equally divided doses (BID). According to when the first dose or last dose is administered, other administration schemes can occur. Hence any patients receiving BRV not divided into 2 equally doses will be reviewed during the DEM to determine whether they are taking BRV per SmPC.
- BRV is administered as an adjuvant therapy, defined as
  - patient receiving at least 1 concomitant AED at Baseline and at each post-Baseline documented visit.
  - patient does not have a protocol violation of Selection Criterion # 6

Modified FAS listings to investigate compliance with the approved SmPC will be created and reviewed at the DEM prior to database lock in order to determine which patients will be included in the modified FAS. If the number of patients in the modified FAS is sufficiently different to

that in the SS, then key demographic, effectiveness and safety tables will be repeated on the modified FAS.

### **3.6 Treatment assignment and treatment groups**

Brivaracetam will be prescribed according to normal clinical practice for all patients in the study. Therefore, there is only 1 treatment group. For this group the label “BRV” is used.

### **3.7 Center pooling strategy**

No pooling of centers is planned for this study as data will be summarized altogether.

### **3.8 Coding dictionaries**

Adverse drug reactions will be coded using version 23.0 or higher of the Medical Dictionary for Regulatory Activities (MedDRA). Medications will be coded using the September 2017 version of World Health Organization Drug Dictionary (WHODD). Medical history is not being collected for this study and concomitant medical procedures will not be coded.

### **3.9 Changes to protocol-defined analyses**

A summary of the change from Baseline to 6 months in individual subtest scores was added to be consistent with the analysis of the EpiTrack total score.

According to the protocol seizure freedom at the end of the Observation Period should be presented. However seizure freedom at the end of the Observation Period will not be presented.

## **4 STATISTICAL/ANALYTICAL ISSUES**

### **4.1 Adjustments for covariates**

There will be no adjustments for covariates.

### **4.2 Handling of dropouts or missing data**

Missing data will not be imputed with the exceptions described below.

#### **4.2.1 Seizure diary**

Seizure data will be recorded at each visit as described in [Section 8.2.2.1](#).

The treating physician will use the patient diaries to calculate the number of seizures since the previous visit and will enter this information into the CRF. Hence, if a patient misses a visit, as long as they have diaries available when they attend the next visit, then the seizure information can still be utilized.

#### **4.2.2 Times and Dates**

Partial dates may be imputed for statistical analyses for specific outcomes according to the following rules. There will be no imputation of missing times. In general, imputed dates will not be shown in listings with the exception of showing imputed dates alongside partial dates for key derivations.

Imputation of partial first BRV administration date:

- If the day of first BRV administration is missing and the month and year are the same as the month and year of Visit 1 then the date of Visit 1 will be imputed as the date of first BRV administration. Otherwise impute 1st of the month.
- If the day and the month of first BRV administration are missing then no imputation of the partial date will be done.

Imputation of partial start dates:

- If only the month and year are specified and the month and year of first dose is not the same as the month and year of the start date, then use the 1st of the month.
- If only the month and year are specified and the month and year of first dose is the same as the month and year of the start date, then use the date of first BRV administration.
- If only the year is specified, and the year of first dose is not the same as the year of the start date, then use January 1st of the year of the start date.
- If only the year is specified, and the year of first dose is the same as the year of the start date, then use the date of first BRV administration.
- If the start date is completely unknown, then use the date and time of first BRV administration.

Imputation of partial end dates:

- If only the month and year are specified, then use the last day of the month.
- If only the year is specified, then use December 31st of that year.
- If the stop date is completely unknown, do not impute the stop date.

The imputation rules should not create an inconsistency in the data.

### 4.3 Interim analyses and data monitoring

No formal interim analyses are planned; however, 3 nonformal interim analyses (snapshot analyses) were performed in order to assess early treatment effectiveness, as follows:

- A first snapshot analysis was to be performed with a data cut-off date approximately at the end of 2016 or when 80 patients have completed Visit 2 (Month 3), whichever occurs first. The snapshot was taken on 05 Oct 2016. All patients with available data in the database were included in the analyses. A subset of the end of study TFLs were produced.
- A second snapshot analysis was to be performed with a data cut-off date approximately at the end of 2017, depending on recruitment status. If the recruitment schedule would have resulted in there not being enough additional data from the previous snapshot then the snapshot cut-off date could have been delayed to ensure approximately 200 patients had Visit 2 (Month 3). The snapshot was taken on 13 Apr 2018. All TFLs identified in the SAP and Mock TFL shells at the time of the snapshot were delivered including all visits available in the database at the time of the snapshot cut off.
- A third snapshot analysis was performed with a data cut-off date on 28 Nov 2019. All TFLs identified in the SAP amendment 3 and Mock TFL shells were delivered including all visits in the database at the time of the snapshot cut off.

As data is entered in an ongoing way throughout the study and cleaning is ongoing, data discrepancies in the snapshot analyses are possible. Any data discrepancies observed in the database at the time of the snapshot analyses were discussed and their impact on the analysis documented.

#### **4.4 Multicenter studies**

The data from different centers will be summarized together.

#### **4.5 Multiple comparisons/multiplicity**

No adjustments for multiplicity will be made as the statistical analyses will be exploratory in nature.

#### **4.6 Use of subsets of subjects**

All effectiveness analysis will be performed on the FAS and the modified FAS to estimate the effectiveness for patients using BRV per the approved SmPC.

In addition, the responder analysis and the seizure freedom analysis will be repeated on the FAS and modified FAS for:

- patients who completed the study
- patients who discontinued the study due to a lack of efficacy

#### **4.7 Active-control studies intended to show equivalence**

Not applicable.

#### **4.8 Examination of subgroups**

- Age at Visit 1 (<65 and ≥65 years).
- Time since first diagnosis of epilepsy (0-<1 years, 1-<5 years, 5-10 years, >10 years): Defined in [Section 6.2](#)
- Number of AEDs at study entry (0, 1, 2, 3 and >3 AEDs) : Defined in [Section 6.4](#)
- Number of Historical AEDs (0 or 1 or 2 or 3, 4 or 5 or 6, >6): Defined in [Section 6.4](#)
- Historical Levetiracetam (LEV) use (Yes, No): Defined in [Section 6.4](#)
- Number of Lifetime AEDs (0 or 1 or 2 or 3, 4 or 5 or 6, >6): Defined in [Section 6.4](#)
- 28-day Baseline all seizures frequency (≤5, >5-10, >10): Defined in [Section 8.2.2.1](#)

The number of patients in the subgroup categories listed above will be examined at the DEM meeting to ensure sufficient patients exist in each category for statistical analysis of the primary and secondary variables by subgroup to offer meaningful analyses. For example, if it is deemed that there are an insufficient number of patients in the ≥65 years age at Visit 1 category, then the age at Visit 1 categories may be amended to use <60 and ≥60 years instead.

## 5 STUDY POPULATION CHARACTERISTICS

### 5.1 Subject disposition

The following tables will be produced on the All Subjects Documented set:

- Disposition of All Subjects Documented. For all study sites and by study site, this table will show the date of the first patient in/last patient out and the number of patients in the All Subjects Documented set, FAS, SS and modified FAS.
- Disposition of Analysis sets to include the number and percentage of patients in the All Subjects Documented set, FAS, SS and modified FAS
- Disposition and Discontinuation Reasons including:
  - Number and percentage of patients completing or prematurely discontinuing the study with discontinuation reason (as recorded in the Study Termination NIS (Dropout) and Study Termination NIS (Completed Subject) CRF pages)
  - Number and percentage of patients continuing or discontinuing BRV after study participation in this NIS with discontinuation reason (as recorded in the Post-Study Treatment Continuation and Medication Discontinuation CRF pages)
- Number and percentage of patients attending each scheduled visit (including mapping of withdrawal visits as described in [Section 3.2.2](#))

In addition to a study eligibility criteria text listing, the following by-patient listings on the All Subjects Documented set will be produced:

- Patients who did not meet study eligibility criteria
- Patient disposition (including first and last BRV dose, completion and early discontinuation information, primary reason for discontinuation, whether the patient is prescribed BRV after exiting the study and the main reason for BRV discontinuation)
- Patient discontinuation (only including patients who discontinue)
- Patient analysis sets
- Patients excluded from analysis sets with reason for exclusion
- Visit dates

### 5.2 Protocol deviations

Important protocol deviations will be identified at the DEMs as described in [Section 3.4](#). The number and percentage of patients in the All Subjects Documented set with at least 1 important protocol deviation and with at least 1 important protocol deviation by deviation type will be summarized. This will include a summary of the number of patients not meeting the selection criteria. The denominator for percentages will be the number of patients in the All Subjects Documented set. A by-patient listing will be presented for all patients in the All Subjects Documented set, and will include the deviation type and description.

## 6 DEMOGRAPHICS AND OTHER BASELINE DISEASE CHARACTERISTICS

All demography, Baseline disease characteristics, and historical and concomitant medication summaries will be presented on the SS and modified FAS, except for subgroup analyses that will only be presented on the SS. Demography will be also presented on the All Subjects Documented set. Listings of all data will be presented on the All Subjects Documented set.

### 6.1 Demographics

The following patient demographics will be summarized.

- Age at Visit 1 (years) – Age will be taken from the CRF and summarized as a continuous variable in addition to the following categories:
  - <65 and ≥65
  - <18 years, ≥18 - <65 years, and ≥65 years (in addition, the ≥65 years category will also be broken down into ≥65 - ≤75, >75 - ≤85, and >85)
  - ≤18 years, >18 - <65 years, and ≥65 years
- Gender (male, female)

A by-patient listing of the date of birth (year only), age, and gender will be provided. If required, the listing will be repeated for patients aged <18 years only.

### 6.2 Other Baseline disease characteristics

The following Baseline disease characteristics will be summarized:

- History of Epilepsy
  - Time since first diagnosis of epilepsy (years)  
(Date of Visit 1 – Date of first diagnosis of epilepsy) / 365.25  
Note that as the day of first diagnosis is not collected in the CRF it will be imputed per the rules outlined in [Section 4.2.2](#). If the time since first diagnosis is greater than the patient's age due to the application of imputation rules, then time since first diagnosis will be set to equal the patient's age. If the time since first diagnosis is less than or equal to 0 due to the imputation rules, then time since first diagnosis will be set to 0.
  - Time since first diagnosis of epilepsy (0-<1 year, 1-<5 years, 5-10 years, and >10 years)
  - Age at time of first diagnosis of epilepsy (years)  
Age – Time since first diagnosis of epilepsy
  - Percent of life with epilepsy  
 $100 \times \text{Time since first diagnosis of epilepsy (years)} / \text{Age}$
  - Reason for initiation of BRV (Behavioral side effects to current AED, Other intolerance to current AED, Lack of efficacy of current treatment, Administer therapeutic dose without titration, or Other): as recorded in the Initiation of Medication CRF form
- Baseline seizure frequency as described in [Section 8.2.2.1](#) summarized as a continuous variable and in the following categories (≤5, >5-10, and >10 seizures per 28-days)

- 28-day Baseline all seizure frequency
- 28-day Baseline POS frequency
- 28-day Baseline POS with secondary generalization frequency
- Epilepsy etiology and seizure classification
  - Whether the etiology of epilepsy is known and the type of etiology as recorded in the Etiology of Epilepsy CRF form
  - Seizure history profile based on the 1981 International League Against Epilepsy (ILAE) Classification. Any POS (I) and each seizure sub type (IA [also broken down into IA1, IA2, IA3, IA4], IB and IC) as recorded in the ILAE Seizure Classification History CRF page

The following by-patient listings will be provided

- History and etiology of epilepsy (including time to first diagnosis, age at first diagnosis, percent of life with epilepsy, etiology, ILAE Seizure classification and reason for BRV initiation)
- Baseline seizure count (including number of all seizures, POS and POS with secondary generalization seizures)

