**Table 17–1: Recommended schedule of study assessments**

Assessments	Visit 1 a Baseline/Day 1 First Day of BRV Treatment	Visit 2 3 Months (Approximately 3 months after Baseline according to routine practice b )	Visit 3 6 Months (Approximately 6 months after Baseline according to routine practice b )	Visit 4 c 12 Months (Approximately 12 months after Baseline according to routine practice b ) End of Observation/ Withdrawal Visit
Recording of AEs	X h	X	X	X
QOLIE-31-P	X	X	X	X
EpiTrack cognition assessment	X		X	X
CGIC		X	X	X
PGIC		X	X	X
Withdrawal criteria		X	X	
Study termination				X

AE=adverse event; AED=antiepileptic drug; BRV=brivaracetam; CGIC=Clinical Global Impression of Change; PGIC= Patient’s Global Impression of Change; QOLIE-31-P=Patient Weighted Quality of Life in Epilepsy Inventory-Form 31

a Visit 1 will be performed after the decision is taken to start adjunctive BRV therapy. Treatment with BRV should be initiated according to routine clinical practice. If the first dose of BRV is given on the same day as Visit 1, it should be administered after Baseline assessments are complete.

b The frequency of visits after Visit 1 will be based on local clinical practice and the patients’ requirements. The clinical procedures performed at each visit will also follow local clinical practice.

c For patients who discontinue early, the treating physician should collect data as specified for Visit 4 as a Withdrawal Visit.

d To include year of first epilepsy diagnosis, lifetime AEDs, etiology. Dates of use of levetiracetam with dosages and reason for discontinuation will be recorded when applicable.

e The treating physician will explain the importance of diary completion to the patient and will review his/her diary at each visit.

f The treating physician will evaluate at each visit the frequency and type of seizures experienced by the patient since the previous study visit. At Baseline, seizure frequency will be based on the previous 3 months to estimate the frequency per 28 days.

g Record name of AED and dose, and any changes after Visit 1.

h Adverse events will be recorded from the moment data consent is obtained.

---

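### SAP 6.2 sends the epilepsy diagnosis date to start-date rules tied to first BRV, so read literally an unknown date becomes zero duration and, if only the year is recorded, most dates shift to 1 January

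*SAP*

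**What the plan says.** SAP 6.2 computes time since first diagnosis as Visit 1 date minus diagnosis date, divided by 365.25. It notes that "as the day of first diagnosis is not collected in the CRF it will be imputed per the rules outlined in" Section 4.2.2 and gives no rule specific to diagnosis. Values above the patient's age are set to age. At the lower end, if the result "is less than or equal to 0 due to the imputation rules, then time since first diagnosis will be set to 0". Age at diagnosis and percent of life with epilepsy are derived from the same quantity.

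SAP 4.2.2 has three blocks: first BRV date, partial start dates and partial end dates. The relevant start-date rules are:

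- Completely unknown: "If the start date is completely unknown, then use the date and time of first BRV administration".
- Year only, when it differs from the first-dose year: the instruction is "then use January 1", meaning the first day of the recorded year. If the years match, the first BRV date is used.
- Month and year: the 1st of the month, or the first BRV date if it falls in that month.

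Protocol Table 17–1, note d, describes the epilepsy history to be collected: "To include year of first epilepsy diagnosis, lifetime AEDs, etiology".

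SAP 4.8 lists the subgroup "Time since first diagnosis of epilepsy (0-<1 years, 1-<5 years, 5-10 years, >10 years): Defined in" Section 6.2. SAP 8.1.3 repeats 12-month retention in each subgroup. SAP 8.2.2.3 does the same for absolute reduction in partial-onset seizure frequency and for seizure freedom.

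**The concern.** First BRV is a sensible anchor for dates that may fall near the start of treatment. A diagnosis of epilepsy usually precedes adjunctive treatment, so the first BRV date is an implausible default for a diagnosis date that nobody knows. The rule turns missing information into the shortest possible duration. Because the value is then no longer missing, the missing row that SAP 3.1 would otherwise add does not appear, and the reader of the table cannot see what happened.

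The year-only rule has a different effect. It moves dates to the start of the year, so durations are overstated and some patients cross a subgroup boundary, always towards longer duration.

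At stake are the time-since-diagnosis rows of the subgroup tables, the 0-<1 year row above all, and three Baseline summaries: time since diagnosis, age at diagnosis and percent of life with epilepsy.

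**Working it through.** The plan gives no figure for diagnosis-date imputation. Its one design figure reproduces (1.95996² × 0.25 / 0.05² = 384.1, hence 385) but does not enter here.

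**Inputs.** V = Visit 1 date, F = first BRV date, D = diagnosis date; t = (V − D)/365.25, floored at 0 and capped at age (SAP 6.2). Cut points are 1, 5 and 10 years (SAP 4.8). V is on or before F, since Protocol Table 17–1, note a, puts Baseline assessments before the first dose.

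**Assumptions, not in the documents.** V = F, spread evenly over one calendar year; diagnosis dates spread evenly; true duration uniform on 0–15 or 0–40 years. The 4.2.2 rules were applied literally to simulated dates.

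**1. Completely unknown date.** D is set to F, so t = (V − F)/365.25 ≤ 0 and is floored at 0. Age at diagnosis = age − 0 = current age. Percent of life = 100 × 0 / age = 0. The subgroup is always 0-<1 year.

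Let u be the share of patients with an unknown date, and s the share truly under 1 year among the rest. Unknown-date patients then make up u / [u + (1 − u)s] of the 0-<1 year subgroup. Neither u nor s is given; over an assumed range:

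| u | s = 2% | s = 5% | s = 10% |
|---|---|---|---|
| 1% | 33.6% | 16.8% | 9.2% |
| 3% | 60.7% | 38.2% | 23.6% |
| 5% | 72.5% | 51.3% | 34.5% |
| 10% | 84.7% | 69.0% | 52.6% |

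For example, 0.01 / (0.01 + 0.99 × 0.10) = 9.2%, and 0.10 / (0.10 + 0.90 × 0.02) = 84.7%.

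**2. Year only, before the first-dose year Y.** D becomes 1 January. Example: V = 15 Mar 2018, D = 20 Nov 2017. True t = 115/365.25 = 0.31 year. Imputed t, from 1 Jan 2017, = 438/365.25 = 1.20 years, so the patient moves from 0-<1 to 1-<5.

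| Diagnosis year | Mean shift | Subgroup changed |
|---|---|---|
| Y−1 | +6.0 months | 50% |
| Y−5 | +6.0 months | 50% |
| Y−10 | +5.9 months | 49% |
| Y−2, Y−4, Y−6, Y−9, Y−11 | about +6.0 months | 0% |

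By true subgroup, about 50% of the under-1-year group move up, 12.5–12.9% of 1-<5 and 9.8% of 5-10. Over all year-only patients, 10.0% (0–15 years) or 3.8% (0–40 years) are misplaced. Arithmetic agrees: each cut displaces half of the one-year band below it, and 3 × 0.5 = 1.5 years gives 1.5/15 = 10.0% and 1.5/40 = 3.75%.

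**3. Year only, same year as first dose.** D becomes F, so the date moves later, by 3.0 months on average and at most 11.8. The value is 0 and the subgroup does not change.

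**4. Month and year recorded.** The mean shift is 0.5 month. Overall 0.8% (0–15 years) or 0.3% (0–40 years) are misplaced, and 4–5% of the true under-1-year group.

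**5. With mid-period rules** (mid-year, or the midpoint between 1 January and first BRV in the first-dose year):

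| Year-only dates | Current rule | Mid-period |
|---|---|---|
| Misplaced, 0–15 years | 10.0% | 5.0% |
| Misplaced, 0–40 years | 3.8% | 1.9% |
| True under 1 year moved up | about 50% | about 12.5% |
| Mean shift | +5.7 to +5.9 months | about +0.1 month |

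Under the mid-period rule about 3% of the true 1-<5 group move down into 0-<1. For month-year dates, misplacement falls from 0.8% to 0.4%, or from 0.3% to 0.2%.

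**The case against.** The strongest answer is that SAP 6.2 speaks only of the uncollected day. That describes a CRF holding month and year, and the error is then small (step 4). Table 17–1, note d, is a list of history items, not a CRF specification, and does not exclude the month. This stands: the year-only figures are conditional. A reader might infer that half of recently diagnosed patients will be misplaced, but the documents do not establish that only the year is recorded.

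Second, 6.2 does not itself say that a wholly unknown date is to be imputed. SAP 4.2 leaves missing data unimputed apart from listed exceptions, and 4.2.2 opens by speaking of partial dates. The floor at 0 has an innocent use as well: a diagnosis in the month of first dose is imputed to first BRV, and 0 is then nearly right. So the floor does not show that unknown dates were meant to become zero. What remains is that the completely unknown start date is one of the rules in the section to which 6.2 refers, with nothing to exempt diagnosis. In the same section the SAP declines to impute a first BRV date whose day and month are both missing, so leaving a date missing would not be foreign to it.

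Third, no counts are given, and a fully unknown diagnosis date may be rare. This stands too; the table in step 1 shows a range, not an estimate.

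Fourth, the analyses are descriptive, and subgroup sizes are reviewed at the data evaluation meeting. The planned review of subgroup sizes concerns the number of patients per category, not how their dates arose. The closing sentence of 4.2.2, against creating inconsistencies, gives no operational rule.

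**Conclusion.** The point holds in a limited form. For a completely unknown diagnosis date, the literal rule gives zero duration and an unwarranted place in the 0-<1 year subgroup. The effect on that row could be slight or dominant, depending on counts that the documents do not give.

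For partial dates, the size depends on the CRF. If only the year is recorded, dates before the first-dose year shift by about 6 months towards longer duration, and about half of patients diagnosed in Y−1, Y−5 and Y−10 change subgroup. If month and year are recorded, the shift is about half a month and under 1% are misplaced overall. These figures assume evenly spread dates and the uniform durations stated in the working.

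Two further inferences are tempting and not supported. One is that the primary result is biased: overall 12-month retention under SAP 8.1.1 uses first BRV, last BRV and study termination dates, not the diagnosis date. The other is that all year-only dates are pushed early: those in the first-dose year are pushed late, without a subgroup error.

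**What to change.** In SAP 6.2, replace the reference to 4.2.2 with a rule for the diagnosis date:

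- Completely unknown: time since diagnosis is missing. Show the patient in a missing row and leave the patient out of that subgroup table. Age at diagnosis and percent of life with epilepsy are then missing as well.
- Year only: impute mid-year, or the midpoint between 1 January and Visit 1 if the year is that of Visit 1.
- Month and year: impute mid-month.
- In every case, not after Visit 1 and not before birth.

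Also reconcile Protocol Table 17–1, note d (year), with SAP 6.2 (day not collected). A look at the CRF field settles which case applies.

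The cost is a few lines of SAP text and code, and some patients, probably few, move to a missing row. Mid-year imputation does not remove the misclassification of year-only dates: about half of the current amount remains, now in both directions.
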